#### Cohort B:

A Simon's 2-stage optimal design will be used to investigate the primary endpoint in patients with active infection and/or end organ disease. The boost treatment strategy will be considered promising for further investigation if 35% achieve objective recovery at 100 days. However, if 10% or fewer achieve sustained recovery, the strategy will not be considered promising. Based on these rates, the trial will accrue a maximum of 19 patients. In the first stage of the trial, response will be evaluated in the first 11 patients. The trial will stop due to a lack of efficacy if one or no patient achieves objective recovery; otherwise, an additional 8 will accrue. At the end of the trial, if at least 4 out of the 19 patients achieve an objective recovery at 100 days, the boost intervention will be considered promising for further investigation. The type I and type II errors are both set at 0.10.

The estimated accrual is 4-5 patients/year and the overall study duration is 4-5 years.

Amended: 02-DEC-2015

Page 17 of 24

The Cohort B trial includes early termination in the event that patients have high rates of grade III-IV acute GVHD. The stopping rules below are based on a maximum of 19 patients receiving the boost intervention.

Failure Type	# of failures needed to stop the study	Failure rate in the population	Probability boundary is crossed
Acute GVHD (Grade III-IV)	2 in the first 4 patients	0.10	0.10
	3 in the first 8 patients		
	4 in the first 14 patients		
	5 at any point	0.35	0.89

This trial includes a number of secondary objectives that will be explored separately for the two cohorts.

1. The objective count recovery will be tabulated by the severity of PGF at the time of the boost.
2. Overall survival following the TCD boost will be estimated using Kaplan-Meier methodology.
3. The incidence of grade II-IV and III-IV acute GVHD and chronic GVHD will be estimated using cumulative incidence functions. Competing risks for these events include relapse and non-relapse mortality.
4. The frequency of serious infections as defined by CIBMTR will be tabulated for the two patient cohorts.
5. The levels of T-cell chimerism will be compared for patients who do and who do not achieve the 100-day objective count recovery endpoint.
6. Immune reconstitution will be explored using graphical and descriptive measures.

As outlined in section 10.1, this trial includes a number of correlative studies. These studies will be performed and analyzed in [name] lab.

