### 3.3 TCD stem cell boost for Poor graft function

A retrospective analysis of patients who were treated for severe PGF at MSKCC identified 35 patients who underwent allogeneic TCD boost of either peripheral blood (N=14) or bone marrow (N=21) stem cells; all boost grafts were from the original donors, without any further pre- boost conditioning therapy. The etiologies for PGF in this group of patients included infections (N=17), GVHD (N=12), low cell dose (N=2) and idiopathic (N=5). The median time between the first transplant and the TCD boost was 4.5 months (0.7-90.7 months). 7 patients died early post TCD boost (within the first 28 days post boost) and were not evaluable for blood count recovery.

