Objective improvement in counts ( $ANC > 0.5 \times 10^9/L$  without G-CSF support and  $Plt > 50 \times 10^9/L$ ) occurred in 20 patients with a median of 3.4 months (range 0.36–22.2 months) post TCD boost. In 17 out of the 20 patients there was further improvement of peripheral blood counts ( $ANC > 1.0 \times 10^9/L$  and  $Plt > 100 \times 10^9/L$ ) with median of 8.8 months. For the 20 patients who had objective improvement in counts, the median cell dose was  $1.8 \times 10^7$  SBA-E- cells/kg when bone marrow, HPC(M) was used as source of stem cells and  $6.7 \times 10^6$  CD34+ cells/kg for patients who received HPC(A) TCD boost. Among the other 8 patients who were alive post day 28 after the TCD boost and had persistent poor graft function without objective improvement in blood counts, 2 had ongoing GVHD and in the other 6 patients the lack of response was of unknown reason. The stem cell boost infusion was well tolerated in all patients and no grade 2 or higher adverse events were reported. New onset GVHD, acute or chronic, was not documented in any of the patients, however, GVHD flare was documented in 2 patients with preexisting GVHD. The 2 and 5 years survival post TCD boost were 48.6% and 37.1%, respectively. The median survival for patients who achieved minimal objective count recovery was 77.58 months and for those who achieved optimal count recovery 80.34 months as compared to 6.61 months for patients who had no peripheral blood counts recovery. The 2 years OS for patients with peripheral blood counts recovery was 90% as compared to 18% for patients without counts recovery. Patient's medical condition at time of TCD boost administration had significant impact on response to treatment and survival. The best outcomes were seen in patients with no evidence of end-organ dysfunction (defined as creatinine > 2, total bilirubin > 2, need for mechanical ventilation and active infection) and who were still outpatients. In this group of patients 56% were alive and with stable peripheral blood counts on day 100 post administration of TCD boost as oppose to the other group of patients where only 10% were alive and with stable counts.

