### 14.0 BIOSTATISTICS

This protocol investigates the efficacy of T-cell depleted boosts for poor graft function (PGF) in two cohorts of patients. The first cohort is patients who have PGF without any active infection, GVHD, and end organ compromise at the time of TCD boost administration (Cohort A). The second cohort is patients who have PGF with active infection, GVHD, or end organ compromise at the time of TCD administration (Cohort B). The protocol will have two single-arm phase II trials to investigate the efficacy separately in the two cohorts. The primary endpoint in both cohorts is the achievement of objective count recovery as defined in section 12.0 at 100 days following the intervention without the aid of growth factors. Patients who die prior to 100 days or those who achieve count recovery but lose their counts prior to 100 days will be treated as treatment failures.

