#### Cohort A:

A Simon's 2-stage optimal design will be used to investigate the primary endpoint in patients without active infection or end organ disease. Based on historical MSKCC data, the boost treatment strategy will be considered promising for further investigation if 65% achieve objective recovery at 100 days.

However, if 40% or fewer achieve sustained recovery, the strategy will not be considered.

promising. Based on these rates, the trial will accrue a maximum of 28 patients. In the first stage of the trial, response will be evaluated in the first 13 patients. The trial will stop due to a lack of efficacy if 5 or fewer achieve objective recovery; otherwise, an additional 15 will accrue. At the end of the trial, if at least 15 out of the 28 patients achieve an objective recovery at 100 days, the boost intervention will be considered promising for further investigation. The type I and type II errors are both set at 0.10.

The estimated accrual is 7-10 patients/year and the overall study duration is 3-4 years.

The Cohort A trial includes early termination in the event that patients have high rates of grade III-IV acute GVHD. The stopping rules below are based on a maximum of 28 patients receiving the boost intervention.

Failure Type	# of failures needed to stop the study	Failure rate in the population	Probability boundary is crossed
Acute GVHD (Grade III-IV)	3 in the first 8 patients	0.10	0.09
	4 in the first 14 patients 5 in the first 20 patients 6 in the first 27 patients 7 at any point		
		0.35	0.96

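### Should Section 14.0 add an analysis of time to count recovery, or of recovery after day 100, when half of the historical improvers took 3.4 months or longer?

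*Combined protocol and SAP*

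**What the plan says.** Section 14.0 makes the primary endpoint in both cohorts "the achievement of objective count recovery as defined in section 12.0 at 100 days". Death before day 100, or recovery lost before then, counts as failure. The Cohort A target is on the same scale: the boost is promising "if 65% achieve objective recovery at 100 days". Cohort B uses 35%, also at day 100.

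Six secondary analyses follow the Cohort B text in Section 14.0. Two use count recovery:

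- Item 1: "The objective count recovery will be tabulated by the severity of PGF at the time of the boost". No time point is named.
- Item 5: "The levels of T-cell chimerism will be compared for patients who do and who do not achieve the 100-day objective count recovery endpoint".

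Kaplan-Meier estimation is planned for overall survival and cumulative incidence for GVHD. Neither is planned for count recovery.

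On data, the assessment table in Section 10.0 ends at day 100, with a window of 7 days either side for that visit. Section 9.0 continues blood counts every 2 to 4 weeks after day 100 for patients with partial recovery. Section 12.0 does not define that term.

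Section 3.3 gives the history. Of 35 patients boosted, "7 patients died early post TCD boost", within 28 days. Improvement "occurred in 20 patients with a median of 3.4 months" (range 0.36 to 22.2 months). For patients in better condition, "In this group of patients 56% were alive and with stable peripheral blood counts on day 100 post administration of TCD boost"; in the remaining patients the figure was 10%.

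**The concern.** The historical median falls just after the day on which the trial reads its endpoint. The series also used a milder rule than Section 12.0: ANC above 0.5 without G-CSF and platelets above 50, against ANC above 1.0, platelets above 50, and haemoglobin and reticulocyte conditions, all without support. In the same patients, recovery by the Section 12.0 rule could not come earlier than improvement by the series rule.

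A patient who recovers in month 5 and one who never recovers would therefore both fail the primary endpoint, and no secondary analysis is stated to separate them. If a cohort missed its target, the planned report would not say how many patients recovered later. Section 3.4 also mentions the chance to study the natural history of poor graft function prospectively, yet no analysis describes counts after day 100. At stake is the reading of a negative result: a treatment that works slowly could look the same as one that does not work.

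**Working it through.** **1. The plan's own designs.** For a Simon design with first stage n1, stopping at r1 or fewer responses, and success at r or more of n:

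P(promising) = sum over x > r1 of P(X1 = x) × P(X2 ≥ r − x), with X1 ~ Bin(n1, p) and X2 ~ Bin(n − n1, p).

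| Cohort | n1, r1, n, r | At the unpromising rate | At the promising rate |
|---|---|---|---|
| A | 13, 5, 28, 15 | 0.093 at 40% | 0.904 at 65% |
| B | 11, 1, 19, 4 | 0.099 at 10% | 0.909 at 35% |

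Both meet the stated errors of 0.10. A search for the smallest expected sample size under the unpromising rate returns the same two designs.

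**2. Where the median falls.** 3.4 × 30.44 = 103.5 days, or 3.4 × 30 = 102 days. With rounding (3.35 to 3.45 months, at 30.44 days) the range is day 102.0 to 105.0.

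**3. Later improvers with a cut at exactly day 100.** The median of 20 values is the mean of the 10th and 11th. If it exceeds day 100, the 11th value does too, so k, the number improved by day 100, is at most 10. The share of those not improved at day 100 who improve later is (20 − k)/(35 − k). At k = 10 this is 10/25 = 40%. Leaving out the 7 early deaths, it is (20 − k)/(28 − k) = 10/18 = 56%.

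**4. Why 40% and 56% are not safe minima.**

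- *Visit window.* The visit runs from day 93 to day 107, and the median lies inside it. By day 107, up to 19 of the 20 could have improved (one took 22.2 months). The later share is then 1/16 = 6%, or 1/9 = 11% without the early deaths. By day 93, as few as 1 might have improved (the shortest time, 0.36 months, is about day 11). The share is then 19/34 = 56%, or 19/27 = 70%.
- *The other historical figures.* Suppose the 56% and 10% groups together make up the series, which the documents do not say. Under ordinary rounding the only split of 35 is 14/25 and 1/10, giving 15 patients stable at day 100. The only split of the 28 surviving past day 28 is 10/18 and 1/10, giving 11. Both exceed the limit of 10 from step 3. With 15 the later share is 5/20 = 25%; with 11 it is 9/24 = 38%. Group sizes are not given and *stable* is not defined for the series, so the two sets of figures may not be comparable.

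**5. Effect on the decision.** If the day-100 rate in Cohort A were the historical 56%, P(promising) would be 0.640, against 0.904 at 65%. An added description of late recovery would change neither figure.

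**6. Objectives against analyses.** Section 2.0 lists six secondary objectives: recovery by severity, survival, GVHD, infections, T-cell chimerism and immune reconstitution. Section 14.0 lists six analyses in the same order. None of the objectives concerns time to recovery.

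**The case for a change.** The best case for a change is that it would cost little: a descriptive cumulative incidence of recovery, from routine counts and transfusion records in at most 28 + 19 = 47 patients, with the endpoint, sample size and decision rules untouched. The historical headline, 20 of 35, counts recovery at any time, and the trial plans no matching figure. Without a rule set in advance, the choice of which late counts to report would be made after the results are known. A negative result is quite possible: at a day-100 rate of 56%, Cohort A would miss its target with probability 1 − 0.640 = 0.36.

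Most of this is true as fact. Section 14.0 does not state such an analysis, and it would be informative. Three things limit its force.

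- **Attribution.** Sections 3.1 and 9.0 describe, respectively, recovery after an insult is removed and continued monitoring; with no control group, late recovery could not be credited to the boost. It would not rescue a cohort that missed its target.
- **Transfer of the timing.** In the series, "The median time between the first transplant and the TCD boost was 4.5 months" (range 0.7 to 90.7 months), whereas Section 3.4 aims to boost as early as possible. The series had severe disease, while Section 6.1 admits milder cytopenia. In the series 21 of 35 received marrow, with a dose reported in SBA-E- cells; Section 5 uses CD34 selection for both sources.
- **Precision.** Approximate 95% half-widths, 1.96 × √(p(1 − p)/n), are 18 points for n = 28 at p = 0.65 and 21 points for n = 19 at p = 0.35.

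Nor is the gap absolute. Item 1 names no time point, counts continue for partial recoverers, and all patients are followed under the centre's transplant guidelines. The data would probably exist, and an analyst could summarise them and label the summary descriptive.

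**Conclusion.** No change is needed. It is correct that Section 14.0 states no analysis of time to recovery or of recovery after day 100, and that the historical median lies at about day 102 to 105. But day 100 is a legitimate time point, the targets are set on it, and both designs hold their stated error rates. The secondary analyses cover every secondary objective, and Section 3.4 speaks of an opportunity to study natural history without making it an objective.

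The size of the issue is uncertain. Taking day 100 exactly, at least half of the 20 improvers came later. Allowing for the visit window, the later share among those not improved runs from about 6% to 56% of patients including early deaths. The day-100 figures for the two condition groups point to about 25% or 38% if those groups cover the series. All of this rests on pooled retrospective data with a milder rule, and may not carry over to earlier boosts.

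A descriptive summary of late recovery is a reasonable option for the report. Its absence from the plan alters no decision, error rate or planned conclusion.

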### **Secondary objectives:**

1. To explore count recovery by the severity of PGF at the time of the TCD boost
2. To evaluate overall survival after administration of the TCD boost.
3. To assess the incidence of acute and chronic GvHD after administration of the TCD boost.
4. To assess the frequency of infections after administration of the TCD boost
5. To assess the effect of the TCD boost on donor T cell chimerism.

6. To characterize the trend of immune reconstitution after administration of the TCD boosts.

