## 4.2 Intervention

Patients who are diagnosed with poor graft function will be given TCD boost without prior preparative therapy. Patients will be assigned to one of two groups based on their medical condition at time of boost administration: (A) patients who are free of active infection and GVHD and without end organ dysfunction and (B) patients with active infection, active or prior history of GVHD and/or end organ damage.

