### 6.1 Subject Inclusion Criteria

1. Persistent cytopenia requiring growth factors and/or blood products AND evidence of hypocellular BM (<25%). Persistent cytopenia (at least 4 week period) is defined by presence of TWO of the following:
  1. ANC <1.0x10^9/L without filgrastim support or any ANC value that requires recurrent support by filgrastim (administered at least once a week).
  2. Plt<50x10^9/L
  3. Hb<8 or PRBC transfusion dependent (once every 2 weeks or more) with reticulocyte count of < 40x10^9/L.

This criteria for persistent cytopenia and hypocellular bone marrow does not apply to patients with auto-immune cytopenia (category #3 in Section 6.0), ONLY PGF patients.

2. Full donor myeloid chimerism. Patients after T cell depletion transplant can have a significant mixed T cell chimerism and this can affect the testing of marrow chimerism. In this case, the neutrophil chimerism will be used to determine eligibility for this trial. Patients will be excluded if neutrophils are less than 90% donor cells; a higher percentage of host cells could be due to relapse or impending relapse.
3. Age: pediatrics and adults patients. No age exclusion.
4. Each patient must be willing to participate as a research subject and must sign an informed consent form.

5. For infections and end organs related criteria (at time of TCD boost administration) see table below:

Criteria	Arm A	Arm B
Infections	Without active uncontrolled bacterial, fungal or viral infection. CMV - If CMV viremia is <137 IU/ml, but patients are on therapy for CMV. HHV-6 < 40,000 copies/ML and without active trend up.	No limitation
Karnofsky/Lansky performance scale	>60%	No limitation
GVHD	Without evidence of active or prior history of GVHD.	Patients with active GVHD, or with GVHD controlled by steroids or other immunosuppressive medications
Renal function	Creatinine Clearance >60ml/min	No limitation
Hepatic function	Liver enzymes (<x3 ULN), Bilirubin (<x2 ULN) and stable in the 30 days prior to TCD boost	No limitation
Cardiac function	No evidence of uncontrolled heart failure or active angina	No limitation
Pulmonary function	Spontaneous breathing, not requiring ventilatory support.	No limitation

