## 9.0 TREATMENT/INTERVENTION PLAN

1. CBC will be checked weekly for the first two months or until independent of G-CSF and transfusion support, then every two weeks (or more frequently if clinically indicated ) until day 100 post TCD stem cell boost. In patients who by day 100 have partial recovery, monitoring blood counts will continue every 2-4 weeks.
2. Bone marrow aspirate and biopsy for assessment of engraftment will be done approximately on day 28 (+/- 7 days) and day 100 post TCD boost (+/- 10 days) and afterwards as required per BMT guidelines.
3. Peripheral blood lymphocyte phenotyping and in-vitro response to mitogen will be assessed on day 28 and day 100 post TCD boost and afterwards as part of routine post transplant assessment until CD4 reaches 200 and PHA>100th percentile.

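### Cohort B mixes patients with and without GVHD at the boost, but the planned GVHD summary gives one whole-cohort cumulative incidence per endpoint, so it blends new onset with flare or recurrence

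*Combined protocol and SAP*

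**What the plan says.** The third secondary objective in Section 2.0 is "To assess the incidence of acute and chronic GvHD after administration of the TCD boost". The matching analysis, item 3 of the secondary list in Section 14.0, reads "The incidence of grade II-IV and III-IV acute GVHD and chronic GVHD will be estimated using cumulative incidence functions". Relapse and non-relapse mortality are the competing risks. The list is to be explored separately for the two cohorts, and item 3 names no other split.

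Three places define who is in Cohort B:

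- Section 14.0: "patients who have PGF with active infection, GVHD, or end organ compromise at the time of TCD administration (Cohort B".
- Section 4.2: "B) patients with active infection, active or prior history of GVHD and/or end organ damage".
- Section 6.1, GVHD row for Arm B: "Patients with active GVHD, or with GVHD controlled by steroids or other immunosuppressive medications".

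The Arm A entry in the same row of Section 6.1 is "Without evidence of active or prior history of GVHD".

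On history, Section 3.3 states that no new-onset acute or chronic GVHD was documented in the 35 retrospective patients, but that "GVHD flare was documented in 2 patients with preexisting GVHD". Section 17.0 repeats both facts under risks.

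On data, Section 8 lists a GVHD assessment before the boost, and Section 12 collects acute GVHD data weekly to day 100. The GvHD row of the Section 10 schedule is marked from day 14 onward, with no mark at Pre-treat or day 7, and its footnote 5 starts assessment at engraftment.

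**The concern.** Confirming safety is a stated aim of the protocol. For a T-cell depleted boost there are two distinct GVHD questions: does it cause GVHD in a patient who had none, and does it reactivate or worsen GVHD in a patient who already had it? The sponsor answers these separately for its retrospective series. In Cohort B the planned estimate answers neither. Its value depends on how many patients happened to enter with GVHD, and item 3 does not ask for that number. The result could not be set beside either historical finding.

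A flare is a change from a baseline, so the pre-boost grade has to be recorded and assessment has to start early enough. The Section 10 schedule is less clear on both than Sections 8 and 12.

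**Working it through.** **1. Is Cohort B mixed?** Read alone, the Arm B entry in Section 6.1 might suggest that every Arm B patient has GVHD. Section 14.0 joins the entry routes with or, and Section 4.2 with and/or, so a patient with infection or organ compromise and no GVHD also belongs to Cohort B. Patients with GVHD, active or past, cannot enter Cohort A. Cohort B therefore holds both kinds of patient and Cohort A only one.

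**2. Does the plan separate them?** Neither Section 12 nor Section 14.0 gives a flare category, an event definition for a patient with GVHD at the boost, or a stratification by GVHD status. Item 1 of the same list does tabulate count recovery by severity of poor graft function.

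**3. The plan's own GVHD figures.** Item 3 states no figure. The nearest are the Cohort B stopping-rule probabilities for grade III-IV acute GVHD. Exact binomial recursion with boundaries 2 by patient 4, 3 by 8, 4 by 14 and 5 by 19 gives 0.099 at a rate of 0.10 (stated 0.10) and 0.891 at 0.35 (stated 0.89). Both reproduce; this point disputes no figure.

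**4. What pooling hides in the sponsor's series.** Pooled: 2/35 = 5.7%. If the 12 patients with GVHD as a cause of poor graft function were those with GVHD at the boost (an assumption, since that is an etiology count), flare is 2/12 = 16.7% (exact 95% CI 2.1% to 48.4%) and new onset is 0/23 (upper limit 14.8%).

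**5. What pooling would hide in Cohort B.** Let g be the number of 19 with active, controlled or prior GVHD of the type in question. The documents do not give g. The proxy 19 × 12/35 = 6.5 suggests about 7, and the true share could be higher because Cohort A takes no GVHD, so 5, 7 and 10 are shown. Suppose 2 patients, neither already in the event state at the boost, reach an endpoint. Using simple proportions with full follow-up, the pooled figure is 2/19 = 10.5% (exact 95% CI 1.3% to 33%) in every row.

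| g | If both are flares: 2/g | If both are new onset: 2/(19 − g) |
|---|---|---|
| 5 | 2/5 = 40% (5.3% to 85%) | 2/14 = 14% (1.8% to 43%) |
| 7 | 2/7 = 29% (3.7% to 71%) | 2/12 = 17% (2.1% to 48%) |
| 10 | 2/10 = 20% (2.5% to 56%) | 2/9 = 22% (2.8% to 60%) |

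At g = 7 the complementary groups are 0/12 new onset (upper limit 26%) in the first reading and 0/7 flares (upper limit 41%) in the second.

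**6. Denominator effect.** If k of 19 were already in the event state and stayed in the denominator, a 10% rate among the rest would read as 0.10 × (19 − k)/19: 8.9% for k = 2, 7.9% for k = 4, 6.3% for k = 7. That is 0.10 × k = 0.2, 0.4 or 0.7 of a patient.

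**7. Schedule.** Section 8 requires a GVHD assessment before the boost, but the Section 10 GvHD row does not show it. Section 12 has weekly data, but the row starts at day 14 and the footnote at engraftment. Engraftment after the boost is not defined, and Section 9 says: "Bone marrow aspirate and biopsy for assessment of engraftment will be done approximately on day 28 (+/- 7 days").

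**The case against.** **The data can be split later.** GVHD is assessed before the boost, GVHD status is part of arm assignment, and acute GVHD is recorded weekly. This stands. A reader might infer that the trial cannot tell flare from new onset; the documents do not support that. Only the planned summary merges them. What remains is that a flare definition chosen after seeing the data is weaker than one fixed now.

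**The denominator is not stated to be wrong.** Item 3 is silent on whether patients already in the event state are kept at risk, and reading incidence consistently would remove them from both numerator and denominator. A reader might infer a materially diluted rate; that rests on silence and is worth less than one patient (step 6). It carries no weight here beyond a request to state the number at risk.

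**Early flares are largely covered.** The Toxicity row in Section 10 is marked from day 7, Section 11 lists GVHD among the toxicities, and Sections 8 and 12 require the baseline and weekly data. A reader might infer from footnote 5 that early flares would go unseen; taken with these sections, the documents show an inconsistency in the schedule, not a gap in surveillance.

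**The numbers are too small to matter.** Partly right. At g = 7, 2/7 against 0/12 has a Fisher p of 21/171 = 0.12, and at g = 10 the two readings nearly coincide. But the purpose is to describe each harm in the patients who can suffer it, not to test a difference.

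**The whole-cohort grade III-IV estimate is useful.** It matches the 19-patient stopping rule and should not be lost. This stands, so the split should be added to it, not put in its place.

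**Conclusion.** The point holds in a limited form. Followed as written, item 3 gives Cohort B one figure per GVHD endpoint that mixes new onset with flare or recurrence. With 2 events in 19, the same 10.5% could be a flare rate of 20% to 40% with no new onset, or a new-onset rate of 14% to 22% with no flares, for g between 5 and 10. Those ranges rest on assumed values of g, an assumed 2 events and full follow-up.

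It is a minor point, an improvement the sponsor could make. Item 3 is a descriptive secondary analysis. The efficacy decision is untouched, the stopping-rule probabilities reproduce, and Cohort A excludes active and prior GVHD and is unaffected. A reader might infer that the Cohort B safety stopping rule is undermined. Item 3 does not feed that rule, so this point does not show it.

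**What to change.** Keep the whole-cohort estimates in item 3. For Cohort B, add a split by pre-boost GVHD status, taken from the Section 8 assessment and the history, with acute and chronic GVHD classified separately:

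- **New onset.** Cumulative incidence of acute grade II-IV, acute grade III-IV and chronic GVHD among patients with no active, controlled or prior GVHD of that type at the boost, with the same competing risks and the number at risk stated. A first chronic GVHD in a patient with only prior acute GVHD then counts as new onset.
- **Flare, worsening or recurrence.** Among patients with active, controlled or prior GVHD of that type, the number and proportion with an exact 95% CI, and prior deaths shown. For acute GVHD: those who newly reach grade II-IV or III-IV by day 100, among those below that grade at the boost. For chronic GVHD: those whose NIH severity rises above the pre-boost value over available follow-up, among those below the maximum.

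In the Section 10 GvHD row, mark Pre-treat for all patients, as Section 8 already requires. For patients with existing GVHD, also mark day 7 and start assessment at the boost instead of at engraftment, in line with Section 12.

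The cost is an addition to item 3, two schedule marks and one footnote. The baseline assessment, the weekly acute data and the day 7 visit are already planned. The price is precision, with at most 19 patients across both groups: one flare in 5, 7 or 10 patients has an exact 95% CI of 0.5% to 72%, 0.4% to 58% or 0.3% to 44.5%, and no new onset in the other 14, 12 or 9 has an upper limit of 23%, 26% or 34%. The results should be labelled descriptive. Cohort A needs no change to its analysis.

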### 3. Immunologic reconstitution

Our previous studies have identified time points at which the various immunologic functions can be expected to return. Immunophenotyping including CD4/CD8 will be performed on circulating lymphocytes of all patients as well as T cell proliferation in response to PHA at 1 month and 100 days post-TCD boost. These markers will be used to

define immune reconstitution.

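### The analysis for secondary objective 5 relates donor T-cell chimerism to count recovery and omits the change after the boost, which is what the objective asks about

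*Combined protocol and SAP*

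**What the plan says.** Section 2.0, secondary objective 5, reads: "To assess the effect of the TCD boost on donor T cell chimerism". The protocol summary in Section 1.0 lists the same endpoint.

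The matching item in the Section 14.0 list of secondary analyses is: "The levels of T-cell chimerism will be compared for patients who do and who do not achieve the 100-day objective count recovery endpoint". It names no time point, no change from pre-boost and no summary measure. The list is introduced by "This trial includes a number of secondary objectives that will be explored separately for the two cohorts", so the comparison is made within each cohort.

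The data for a before-and-after summary are already planned. Section 8.0 requires lineage chimerism, including T cells, before the boost. The Section 10.0 schedule marks chimerism at pre-treatment, day 28 and day 100. Section 12.0, item 2, gives the post-boost times as 1 month and 100 days.

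No other planned analysis covers the change. The next item in Section 14.0 says "Immune reconstitution will be explored using graphical and descriptive measures", and Section 12.0, item 3, defines that outcome without chimerism: "Immunophenotyping including CD4/CD8 will be performed on circulating lymphocytes of all patients as well as T cell proliferation in response to PHA". The correlative studies in Section 10.1 list progenitor and stroma assays, immune reconstitution and unspecified blood correlatives, with no chimerism analysis.

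**The concern.** Recovery status at day 100 is an outcome that follows the boost. Splitting boosted patients by that outcome shows whether recovery and chimerism go together. It does not show whether chimerism moved after the boost, because both groups were boosted and neither serves as a reference.

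Two errors of interpretation follow. A shift common to all patients is invisible to the contrast. A difference that existed before the boost is carried into it. Such a difference is possible, although the documents do not show one. Section 6.1, item 2, notes that "Patients after T cell depletion transplant can have a significant mixed T cell chimerism", and its 90% donor floor applies to neutrophils, so T-cell chimerism may vary widely at entry.

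The split also depends on the number of responders, which may be very small in Cohort B. If the plan is followed exactly, the report could contain no description of what happened to donor T-cell chimerism after treatment, even though the samples were taken.

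**Working it through.** The documents state no figure for objective 5, so there is none to reproduce. The check has three parts.

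**1. What the planned contrast estimates.** Let B be the mean pre-boost percent donor T cells and Δ the mean change to time t, with R for responders and N for non-responders.

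- Planned contrast at t = (B_R + Δ_R) − (B_N + Δ_N) = (B_R − B_N) + (Δ_R − Δ_N).
- Quantity closest to the objective = mean of the within-patient changes over all sampled patients.

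The values below are illustrative, because the documents give no chimerism data.

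| Case | B_R | B_N | Δ_R | Δ_N | Planned contrast | Mean change |
|---|---|---|---|---|---|---|
| Everyone rises, equal baselines | 60 | 60 | +20 | +20 | 0 | +20 |
| Nobody changes, unequal baselines | 70 | 50 | 0 | 0 | 20 | 0 |

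The contrast can be zero when chimerism moved in everyone, and large when it moved in no one.

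**2. How many responders the contrast would have.** The inputs are the Section 14.0 designs. For Cohort A, with 13 patients in stage 1: "The trial will stop due to a lack of efficacy if 5 or fewer achieve objective recovery"; maximum 28; rates 40% and 65%. For Cohort B, with 11 patients in stage 1: "The trial will stop due to a lack of efficacy if one or no patient achieves objective recovery"; maximum 19; rates 10% and 35%. GVHD stops are ignored.

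Recomputing the two designs with exact binomial probabilities gives type I error 0.093 and power 0.904 for Cohort A, and 0.099 and 0.909 for Cohort B. Both agree with the stated error rates of 0.10, so the rules have been read correctly.

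Probability of a stage-1 efficacy stop:

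- Cohort B, P(X ≤ 1 | n = 11) = (1−p)^11 + 11p(1−p)^10. At p = 0.10: 0.314 + 0.384 = 0.697. At p = 0.35: 0.009 + 0.052 = 0.061.
- Cohort A, P(X ≤ 5 | n = 13): 0.574 at p = 0.40 and 0.046 at p = 0.65.

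A Cohort B trial that continues has at least 2 responders, so 0.697 and 0.061 are also the probabilities of ending with 0 or 1.

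Expected responders at full accrual (N × p):

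- Cohort B: 19 × 0.10 = 1.9; 19 × 0.35 = 6.65.
- Cohort A: 28 × 0.40 = 11.2; 28 × 0.65 = 18.2.

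A change from pre-boost needs no responder split. It can use every patient with a pre-boost and a post-boost sample, up to 19 and 28.

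**3. Deaths.** Section 14.0 counts death before day 100 as treatment failure, but such a patient has no day-100 sample. A day-100 comparison would therefore include only the surviving non-responders. Section 3.3 reports 7 deaths within 28 days among 35 patients (20%), but that series had severe poor graft function and entry under Section 6.1 is broader, so the rate is not carried over. The size of the loss cannot be fixed from the documents, and it limits the change analysis as well.

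**The case against.** **The plan may be broader than it looks.** Item 5 refers to levels and gives no time point. If levels were shown by response group at all three scheduled times, pre-boost values and trajectories would be visible. That is a fair reading of an under-specified sentence, but the stated comparison remains between response groups, and nothing commits the analyst to a comparison over time.

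**The stakes are low.** The objectives are exploratory, no test or decision hangs on item 5, and the stored data allow a change to be reported later. This stands and limits the weight of the point. It does not supply the missing analysis.

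**The responder counts show feasibility, not the mismatch.** This is correct: the same small numbers would affect a responder comparison of change scores. They show how fragile the only planned analysis is. The 0.70 applies if the true rate is 10%; at the design alternative the figure is 0.06.

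**Accrual might run past 11 in Cohort B while stage 1 matures.** At 4 to 5 patients a year, 100 days would add 4 × 100/365 = 1.1 to 5 × 100/365 = 1.4 patients. No pause is spelled out, but Section 14.0 makes the further 8 patients conditional on passing stage 1, so at most one responder follows from the plan as written.

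**A before-and-after change has its own limits.** There is no control arm, deaths remove samples, and a patient already near 100% donor T cells cannot rise. All of this stands. It calls for descriptive wording and for reporting pre-boost levels beside the change.

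**Conclusion.** The concern holds. Section 2.0 asks about chimerism after the boost; Section 14.0 analyses chimerism by recovery status; no other section closes the gap.

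The mismatch follows from the wording and needs no numerical assumption. The 0-versus-20 and 20-versus-0 examples show only what the contrast can return. The stage-1 probabilities rest on the protocol's own design rates, on the efficacy rule alone, and on no enrolment beyond stage 1 before the decision. Cohort A is less exposed, since a stage-1 stop there can still leave up to 5 responders among 13.

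The consequence is confined to one secondary, exploratory objective. The primary endpoint, the Simon designs and the stopping rules are unaffected. The change is worth making because the objective otherwise has no analysis that answers it.

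**What to change.** Replace item 5 of the secondary analyses in Section 14.0 with a paragraph that does the following:

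- Summarises percent donor T cells at pre-boost, day 28 and day 100, and the within-patient change from pre-boost to each later time, separately by cohort. A confidence interval is optional.
- Reports at each time point the number of paired samples and the number of patients not sampled because of death.
- States that without a control arm the change is descriptive, applies to patients alive and sampled, and cannot be attributed to the boost with certainty.
- Keeps the responder comparison as an exploratory association, using change from pre-boost at a named time point, and says that it will not be made in a cohort with 0 or 1 responders.

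The cost is one paragraph. No new samples or visits are needed.
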